Puberty suppression And Transitional Healthcare with Adaptive Youth Services (PATHWAYS)

PATHWAYS – HORIZON: A longitudinal observational study

•	1 T		• 🔑	
Tria		lent	111/	2rc
1114	11 10	wii	ш	OI 3

IRAS:	350909		
ISRCTN:	TBC		
Funder Number:	NIHR167530		
Protocol Version	1.1	Date:	13.06.25
Number:			

Co-Sponsors

Name:	King's College London [name]
	Vice President (Research and Innovation)
Email:	[contact]
Name:	South London and Maudsley NHS Foundation Trust
Email:	[contact]

Chief Investigator

Name:	[name]	
Email:	[contact]	
Signature	[name]	Date: 20/06/2025

Joint Co-Lead

Name:	[name]	
Email:	[contact]	
Signature		Date:

Statistician

Name:	[name]	
Email:	[contact]	
Signature		Date:

Clinical Trials Unit

Name:	King's Clinical Trials Unit
Email:	[contact]

Study Synopsis

Study Synopsis	
TITLE OF STUDY:	Puberty suppression And Transitional Healthcare with Adaptive Youth Services (PATHWAYS). PATHWAYS – HORIZON: A longitudinal observational study
Protocol Short Title/ Acronym:	PATHWAYS-HORIZON
Study Phase:	Longitudinal Observational Cohort Study
Sponsor Name(s):	King's College London and South London and Maudsley NHS Foundation Trust
Chief Investigator(s):	[name] [name] (Deputy CI)
Medical Condition or Disease Under Investigation:	Gender Incongruence
Purpose of Study:	The PATHWAYS HORIZON study aims to address key evidence gaps by reporting on the psychosocial and clinical characteristics of young people referred to the UK CYPGS.
Primary Objective (s):	 To improve the understanding of the care needs and holistic developmental journeys of all CYP attending NHS Gender Services. To understand how the developmental trajectories and short – to medium-term outcomes of CYP with gender incongruence are influenced by differences amongst CYP and their life experiences.
Secondary Objective(s):	 To improve understanding of how care options are experienced by CYP and their parents/carers/legal guardians To develop a novel interview-based outcome measure that focuses on CYP's aspirations and goals from gender care. To explore similarities and differences in the holistic perspectives of CYP and their parents/carers/legal guardians to gain a comprehensive understanding of how gender incongruence affects CYP.
Trial Design:	Longitudinal observational cohort study
Sample Size:	3600 participants
Summary of Eligibility Criteria:	 Inclusion Criteria The CYP has an accepted referral to CYPGS, or has already attended an appointment at a CYPGS. The CYP is awaiting or has received their first appointment with the service at the time of completing baseline measures. Valid assent/consent has been obtained: For CYP under the age of 16 at recruitment providing self-reports:

	i. CYP gives consent to participate. ORii. Personal Consultee gives consent for the CYP
	to participate if the CYP lacks capacity to
	consent.
	c) For parent-reported measures for CYP under the age of
	16 at recruitment: Parent/legal guardian consents to
	their own participation to provide parent-reported measures.
	d) For parent-reported measures for CYP 16 years and
	over at recruitment: Parent/legal guardian consents to
	their own participation to provide parent-reported
	measures and CYP consents to parent/legal guardian completing measures.
	completing measures.
	Exclusion Criteria
	1. CYP did not attend a first appointment at CYPGS.
	2. CYP deemed unsuitable in the opinion of the
	investigator for clinical or other reasons.
Vausian and Data of Final Protects	V1.1 13.06.2025
Version and Date of Final Protocol:	

Revision History

Protocol version	Description of changes from previous revision	Effective Date
Protocol Version 1.0	New Protocol	19.03.2025
Protocol Version 1.1	Informed consent (section 3.3) amended; Inclusion criteria points 3,4,5,6 condensed into one criterion (section 3.2.1); Additional exclusion criterion added (section 3.2.2); Measures/ Data Forms (section 4.4) Primary outcome changed from KIDSCREEN-52 to KIDSCREEN-10; Trauma measure changed from CPSS to APCTSS; new measures Social Transition Questionnaire, Parental 'About Yourself' Questionnaire; validated measures reformatted for online completion and binary language amended to gender neutral language where required; questionnaire items/ response categories added or omitted Annual Health Update, CBCL, YSR, Gender Identity Questionnaire, ASQ, SCOFF, Romantic Relations, Sexual Attraction Questionnaire; DERS-P nonvalidated version changed to validated version; Gender Identity, ASQ and CPSS no longer clinician supported at baseline; Novel Outcome Measure Development (section 4.8) third interview added to assess sensitivity to change; Data security (section 5.2) updated to reflect change in secure storage facilities for personal data; Adverse event collection process (sections 4.5.1, 6) clarified; Statistical Methods (section 8) updated to reflect changes in measures.	13.06.2025

Glossary of terms

ADHD	Attention-Deficit Hyperactivity Disorder
AE	Adverse Event
ALSPAC	Avon Longitudinal Study of Parents and
	Children
ASAI	Adolescent Sexual Activity Index
APCTSS	Adolescent Primary Care Traumatic
	Stress Screen
ASD	Autism Spectrum Disorder
ASQ	Ask Suicide-Screening Questions
BIS-GS	Body Image Scale – Gender Spectrum
CA	Competent Authority
CBCL	Child Behaviour Checklist
CI	Chief Investigator
CRF	Case Report Form
CSV	Comma-Separated Values
CTIMP	Clinical Trial of Investigational
	Medicinal Product
CTU	Clinical Trials Unit
CYP	Children and young people
CYPGS	Children and Young People Gender
	Service
DCR	Data Clarification Request
DERS	Difficulties in Emotion Regulation Scale
DMC	Data Monitoring Committee
eCRF	Electronic Case Report Form
EDC	Electronic Data Capture
ePRO	Electronic Patient Reported Outcomes
GCP	Good Clinical Practice
GP	General Practitioner
GIH	Gender Incongruence History
GnRHa	Gonadotropin Releasing Hormone
	Analogues

IOPPN	Institute of Psychiatry, Psychology
	and Neuroscience
KCL	King's College London
KCTU	King's Clinical Trials Unit
MNAR	Missing Not at Random
NIHR	National Institute for Health and
	Care Research
NPN	National Provider Network
PAGES	Parental Attitudes of Gender
	Expansiveness Scale
PI	Principal Investigator
PIN	Participant Identification Number
PIS	Participant Information Sheet
PMG	Programme Management Group
PSC	Programme Steering Committee
PTSD	Post Traumatic Stress Disorder
RA	Regulatory Agency
RCADS	Revised Child Anxiety and
	Depression Scale
RCT	Randomised Clinical Trial
REC	Research Ethics Committee
CAE	
SAE	Serious Adverse Event
SAP	Statistical Analysis Plan
SCQ	Social Communication Questionnaire
SDW	Source Data Worksheets
SDV	Source Data Verification
SNAP-IV	Swanson, Nolan and Pelhan ADHD
	Rating Scale
TM	Trial Manager
TS	Trial Statistician
UGDS-GS	Utrecht Gender Dysphoria Scale
UK	United Kingdom

PROTOCOL CONTENT

STU	DY SYNOPSIS	2
GLO	SSARY OF TERMS	4
1.	INTRODUCTION	7
1.1	SUMMARY OF PATHWAYS RESEARCH PROGRAMME	8

	8.4.1 STATISTICAL METHODS FOR PRIMARY OUTCOME	
	8.4.2 STATISTICAL METHODS FOR SECONDARY OUTCOMES	
8.5	,	
8.6	(
8.7		
8.8		
8.9		
8.1		
8.1 8.1		
9.	OVERSIGHT AND MONITORING	35
	PATHWAYS PROGRAMME MANAGEMENT GROUP (PMG)	
9.2		
9.3	,	
9.4	Monitoring	35
10.	MISCELLANEOUS	35
10.	.1 Plans for independent audit	35
10.	.2 Publication Policy	35
10.	.3 DISSEMINATION PLANS	36
10.	.4 End of STUDY	36
10.	.5 Confidentiality	36
10.		
10.		
10.		
10.		
10.	.10 Intellectual property (IP)	37
11	REFERENCES	38

1. Introduction

PATHWAYS is a programme of inter-related research studies whose ultimate aim is to improve the care of children and young people (CYP) presenting to clinical services with gender incongruence. **This protocol is specifically for one component of the research, PATHWAYS HORIZON**, which is a longitudinal observational cohort study. However, this general background section starts with a description of the full programme, in order to understand how HORIZON is situated within the programme, and how participants may move from one study to another.

Gender incongruence is characterised by a marked and persistent disparity between an individual's experienced gender and the birth-registered sex, which may lead to a desire to 'transition', to live and be accepted as a person of the experienced gender ¹. Gender incongruence may be more distressing during significant transitional life stages such as adolescence, which can lead to gender dysphoria ².

Until recently, gender incongruence was considered rare ² with limited clinical awareness and service provision. Over the past two decades, changes in the age of presentation, ratio of malefemale birth-registered sex and prevalence of people presenting with gender incongruence have coincided with changes in the available treatment, most notably the use of puberty suppression which had not previously been used for this purpose. Puberty-suppressing hormones or gonadotropin-releasing hormone analogues (GnRHa) came into use in some countries with several potential aims, including reducing feelings of distress with one's body developing secondary sexual characteristics (body dysmorphia) and related emotional distress and making any subsequent physical transition to the opposite gender more straightforward, potentially with less radical surgery. It was also hypothesised that puberty suppression would provide children and young people (referred to hereon as CYP) 'time to think' without further pubertal development to explore gender identity as part of normal adolescent exploration. However, a systematic review ³ reported that 0-8% (including 2% of UK youth ⁴) receiving GnRHa desisted from the treatment and a transitioning pathway ³. This raises concerns about whether the intervention might itself be narrowing rather than increasing perceived choices.

The use of GnRHa became part of routine care in many settings without the standard of rigorous evaluation of benefits and risks, often including randomised clinical trials (RCTs) ³. The increasing use of GnRHa elicited differing and often polarised views about the optimal treatment pathway for CYP with gender incongruence and specifically about the benefits and safety of GnRHa to suppress puberty. Gender incongruence is often a lifelong condition in which the ultimate aim of intervention is to promote long-term well-being and good psychosocial and psychosexual functioning over the life-course. However, there has been a lack of high-quality longitudinal studies with sufficient retention rates to inform clinicians and patients about long-term outcomes, both for those who opt for medical care pathways and those choosing alternatives ³-

Non-medical care for CYP experiencing gender incongruence include psychosocial interventions aimed at exploring gender (and often wider) identity and promoting positive self-esteem, good psychosocial functioning, and well-being. However, non-endocrine intervention for CYP with gender incongruence have similarly not been subjected to rigorous evaluation.

As highlighted below, a substantial proportion of CYP experiencing gender incongruence are neurodiverse and/or have had adverse childhood experiences whose impact on their identity and psychosocial functioning need addressing as part of holistic, comprehensive care. While there is robust evidence for interventions/management strategies around neurodivergence and adverse childhood experiences, their application in the context of gender incongruence may require specific adaptations and bespoke evaluation.

Hence currently decisions about care are made in the context of very limited evidence and against a background of strong personal preferences. This is particularly pertinent for a condition in which intervention decisions rely heavily on the preferences of relatively young children and adolescents who are at a developmental stage intrinsically characterised by exploration of personal identity. Many healthcare professionals and parents have requested more objective clinical evidence to guide decision-making in the interests of longer-term positive outcomes.

1.1 Summary of PATHWAYS Research Programme

The PATHWAYS research programme plans to include five inter-related studies designed to increase our understanding of gender incongruence amongst CYP and its longitudinal course. The full programme is outlined here to provide context for PATHWAYS HORIZON, which is the subject of this protocol.

All the PATHWAYS workstreams, bar PATHWAYS Engagement, involve CYP and their parents/carers/legal guardians who are attending the NHS Gender Services for Children and Young People (CYPGS), or have attended their first appointment.

The overarching aims of the full PATHWAYS research programme are:

- 1. To determine the short/medium-term benefits and risks of GnRHa for puberty suppression, across psychosocial, physical, cognitive and brain outcomes, in CYP with gender incongruence.
- 2. To understand the care needs and experiences of CYP experiencing gender incongruence associated with using GnRHa or not through longitudinal quantitative and qualitative studies.
- 3. To continue to involve CYP with gender incongruence and their parents/carers/legal guardians in designing, implementing and interpreting the research to ensure this study addresses their needs and inform longer-term follow-up.

1.1.1 Studies within the PATHWAYS programme

1.1.1.1 PATHWAYS HORIZON

PATHWAYS HORIZON is an observational cohort (n~3600) of all CYP attending the Children and Young Persons Gender service (CYPGS).

HORIZON participants will be asked to complete questionnaire measures about their experiences, mental health, and quality of life on an annual basis throughout the course of the study. The study will last for the duration of the funding period (5.5 years).

1.1.1.2 HORIZON Intensive

In addition, we will recruit CYP to HORIZON Intensive from the HORIZON cohort who will be broadly matched to those participating in TRIAL, providing a non-randomised comparison group. (Note that "Intensive" refers to research monitoring rather than clinical care.) *The*

PATHWAYS HORIZON Intensive protocol will be included in the PATHWAYS TRIAL protocol and application.

1.1.1.3 PATHWAYS TRIAL

PATHWAYS Trial is a trial of GnRHa in the management of gender incongruence in CYP.

1.1.1.4 PATHWAYS CONNECT

PATHWAYS CONNECT looks at outcomes relating to cognition and brain development in CYP attending the services, including those who are and are not receiving GnRHa.

1.1.1.5 PATHWAYS VOICES

[figure not shown]
PATHWAYS VOICES uses longitudinal qualitative interviews to explore the needs and care experiences of CYP and their families and how these change over the course of time / treatment.

1.1.1.6 PATHWAYS ENGAGEMENT

PATHWAYS ENGAGEMENT is an advisory group of young adults >18 years, adults with gender incongruence, and parents/carers/legal guardians who will advise on all aspects of the programme, including outcome measures, patient involvement in research and strategies for long-term patient engagement, interpretation, and communication of findings. Members of PATHWAYS ENGAGEMENT will meet in person in London and/or online for briefer meetings. NB: As an advisory group of experts by experience, ethical approval will not be sought.

1.1.2 Relationship between PATHWAYS studies

All CYP attending the CYPGS will be eligible for PATHWAYS HORIZON. We anticipate ~80% of CYP will assent/consent to HORIZON. Only CYP who assent/consent (and provide parental consent) to PATHWAYS HORIZON will be approached for PATHWAYS HORIZON Intensive. Many CYP subsequently deemed eligible for and enrolling in PATHWAYS TRIAL will first be members of PATHWAYS HORIZON. Once they join PATHWAYS TRIAL, they will become part of that study and data collection will follow that protocol (rather than the PATHWAYS HORIZON protocol). CYP attending the CYPGS who decline participation in HORIZON but are deemed eligible for PATHWAYS TRIAL may join that study once they provide assent/consent. CYP participating in PATHWAYS Voices are drawn from those in PATHWAYS HORIZON considering GnRHa (and hence may become members of TRIAL). Figure 1 depicts the relationship and participant overlap between studies.

^{*} Those discharged by the service will only be eligible for HORIZON(observational) and would not be eligible for Trial, CONNECT, HORIZON Intensive or VOICES

Figure 1 - Overlap between PATHWAYS participants in different PATHWAYS studies

1.2 Background specific to the PATHWAYS HORIZON Protocol.

Over the past two decades the number of referrals of young people seeking care in gender services has increased significantly $^{6-8}$, with Figure 2 8 depicting the 20-fold increase in UK referrals between 2000 and 2017 .

[figure not shown]

Figure 2. The characteristics of young people seeking support in the United Kingdom (UK) have also changed over this time period. This means that the results of studies reporting on earlier cohorts of CYP may not apply to those currently accessing gender services.

These differences include:

- (1) Markedly increased rates of birth-registered females, shifting from a preponderance of birth-registered males to birth-registered females ^{6, 8};
- (2) Older age of presentation to gender services ⁸, which is therefore associated with more advanced pubertal status;
- (3) A marked increase in CYP who also have neurodevelopmental conditions, particularly autism and possibly attention-deficit hyperactivity disorder (ADHD) ^{9, 10}. The reason for this is presently unclear; it is likely that this represents in part improved recognition of these conditions, but also likely represents a true increase in presentation amongst this group of CYP;
- (4) Increased additional mental health problems, including anxiety, depression and eating disorders ^{11, 12};
- (5) Substantial rates of adverse childhood experiences that are distressing and, in some instances, may lead to post-traumatic stress disorder (PTSD) ^{13, 14}.

Recent changes in the UK service provision established regional children and young people's gender service hubs, referred to as the CYPGS. Currently three services are in place: the London and Northwest hubs and the Bristol centre, and there are plans for a further three or four centres to open over the next two years. These new services include paediatricians, psychiatrists, psychologists, psychotherapists, speech and language therapists, specialist nurses, and occupational therapists working in multidisciplinary teams. A consistent approach has been agreed across services to provide and record a comprehensive assessment of the full range of needs. This assessment leads to a holistic, individualised formulation of each CYP, which is then shared with the CYP and their parents, leading to agreement on a personalised intervention plan. Where possible, evidence-based interventions will be recommended, but as highlighted above, there is a dearth of evidence for treatment efficacy in this population. Consistency of the approach to care is being developed and monitored by a National Provider Network (NPN). Clinicians delivering care in the new services, alongside scientists, healthservice managers and policymakers, want to understand the characteristics of this population, their care needs, and their longitudinal course in relation to gender incongruence, mental and physical health, and quality of life.

The PATHWAYS HORIZON study aims to address these evidence gaps by reporting on the psychosocial and clinical characteristics of young people referred to the UK CYPGS. The study will evaluate a range of characteristics at the time of presentation that may influence management and intervention choices as well as short and longer-term outcomes. PATHWAYS HORIZON will describe outcomes including quality of life, gender identity- and body-dysmorphia-related experiences, mental health, and psychosocial functioning.

2. Study Design

PATHWAYS HORIZON is a longitudinal observational cohort study with an anticipated sample size of approximately 3600 participants (CYP- parent/caregiver dyads). All CYP (and their parents/carers/legal guardians) attending any of the CYPGS will receive information about the study and will be eligible to participate. PATHWAYS HORIZON will run for the duration of the PATHWAYS programme, estimated at 5.5 years. Participants will be recruited into the study for the first 3.5 years. Data will be collected at entry into the service and then on an annual basis until the end of the study. Longer-term follow-up is scientifically important due to the often life-long nature of gender incongruence, and participants will be asked for optional consent to be contacted in the future and for data linkage to health and educational databases. Although participants will be contacted about PATHWAYS HORIZON when they first attend

the CYPGS, they may choose to join the study immediately or later. They can withdraw participation at any time during their attendance in the CYPGS (or afterwards) without affecting their care.

The study will employ a combination of self-report, parent/caregiver-reports and clinician-administered or researcher-supervised scales. Where feasible, the assessments for CYP and their parents/carers/legal guardians should be conducted separately to ensure response validity. Similarly, wherever possible, a 'core' parent informant will be identified, who will be contacted sequentially over time to complete assessments. However, substitution of another parent/caregiver will be allowed within the study protocol.

2.1 *Objectives*

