3.1 Participants

Participants will include CYP of any age referred to the CYPGS, along with their parent(s), caregiver(s), or legal guardian(s) following acceptance of the referral. CYP may be seen in the service up to age 18 years, at which point they are referred to adult Gender Services. Referrals to the CYPGS may be made by an NHS-commissioned secondary care level paediatric service or CYP mental health service. For a referral to be accepted, it must indicate that the CYP is experiencing concerns or distress related to their gender identity. The absence of a lower age limit applies only to the HORIZON study and not to other studies in PATHWAYS which have a greater focus on GnRHa. The purpose of the HORIZON study is to provide a comprehensive description of the presenting characteristics and developmental trajectories of all CYP presenting to the service, in order to improve care for the entire population.

Only CYP and their parents/carers/legal guardians who attend a first assessment appointment in the CYPGS will be included. CYP remain eligible to participate in the study even after discharge from the services, including those who transition to adult services. All CYP and their parents/carers/legal guardians will be followed up annually, even if they no longer remain within the service and/or have been discharged, unless they withdraw from the study.

CYP and their parents/carers/legal guardians who attended a first appointment in the new CYPGS and were discharged prior to the study onset will also be contacted to provide them with the opportunity to participate.

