- 1. The health care team will send the CYP and parent/legal guardian an email explaining that the CYPGS is collaborating with PATHWAYS and asking for their consent for the research team to get in touch to tell them about the study ("consent for contact"). This will ordinarily be sent with information about the first appointment but will be sent separately for those who have already attended a first appointment.
- 2. For those participants who agree to be contacted, the health care team (clinic) will notify the research team who will send the PIS and assent/consent, with their details. They may speak to a researcher in person at the CYPGS, by telephone or MS Teams video call to answer any questions.
- 3. The health care team at the CYPGS will maintain a screening log of participants contacted and their response. For those not providing consent for contact, their file will be flagged at the first appointment. A member of the health care team will then check whether they have considered the consent for contact and chosen not to consent, whether this had not been considered, or they had neglected to respond (as is the experience in other services operating a consent for research contact policy). An anonymised copy of the screening log containing CYP age at referral, length of time on the waiting list, birth-registered sex, ethnicity, index of multiple deprivation decile, known neurodevelopmental diagnosis and whether a member of the health care team requested the CYP was not contacted/included in the study will be shared with the PATHWAYS HORIZON research team in order to understand selective research uptake.
- 4. There will be a small number of participants who have previously attended and been discharged from the CYPGS. They will receive the same email regarding consent for contact. If they do not respond, they will receive one phone call from the clinic to check whether they have received and read the letter and to record their preferences. For those consenting to contact, the same procedure will be followed.
- 5. When the CYP <16 years provides assent but parental consent is lacking, a member of the health care team in the CYPGS will get in touch to remind them that parental consent is required. CYP and parents/carers/legal guardians who have not responded may be contacted by a researcher or clinic administrator to ensure they have received the materials.

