- 6. Informed consent from one parent/legal guardian for CYP under 16 years and consent from CYP 16 years and older will be obtained prior to completion of baseline measures. This consent will be taken separately for CYP self-report and parental report. There is no upper time limit for CYP and their parents/carers/legal guardians to consider participation and they will be encouraged to ask any further questions about the study, including referring to the study website which will develop a section specifically for study participants.
- 7. It is possible there will be rare instances in which the CYP wishes to participate but the parent/legal guardian does not provide informed consent. In such instances, consideration of the CYP's ability to provide informed consent will be delayed until they have been assessed in the CYPGS. The clinical keyworker or their clinical delegate will be requested to assess the CYP's ability to provide informed consent and to consider any disadvantages for their clinical care if they participate against parent support (e.g., family disharmony). The clinician's opinion regarding the CYP's ability to provide informed consent will be recorded in the clinical notes. If they deem the CYP able to provide consent, they will provide an additional signature on the

consent form. Professionals conducting an assessment will have access to training and consultation from a Consultant Paediatrician or Psychiatrist based in the CYPGS.

Study participation will routinely be recorded in the participant's medical record unless a risk is identified. In such cases, the local risk protocol will be followed, which may lead to CYPGS triggering safeguarding or other referrals as necessary at the local site.

Families with CYP unable to complete the baseline assessments, e.g., due to significant intellectual disability, will still be invited to participate in completing parent-reported and clinician-recorded measures. Families with parents/carers/legal guardians who are unable to complete study questionnaires will still be allowed to participate in the study provided they can provide informed written consent, for the CYP (if less than 16 years) to take part in the study.

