3.4 Assessments and assessment windows

Initial data collection for new cases will be at baseline, defined as just before the first appointment, on the day of the first appointment, or within five months of the first appointment. Subsequent data collection will take place annually, with timing related to the initial assessment in the CYPGS. CYP and parents/carers/legal guardians who decline/defer participation at initial contact may join PATHWAYS HORIZON at a later date, which will include baseline characterisation.

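### Questionnaire values described as presenting status may be collected up to five months after the first appointment, at no stated limit for deferred joiners, or after discharge, and the primary model terms do not distinguish these cases

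*Protocol*

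**What the plan says.** Three places describe when characteristics are measured, and all point to arrival in the service.

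- Section 1.2: "The study will evaluate a range of characteristics at the time of presentation that may influence management and intervention choices".
- Section 2: "Data will be collected at entry into the service and then on an annual basis until the end of the study".
- Section 3.1 gives the purpose of HORIZON as "to provide a comprehensive description of the presenting characteristics and developmental trajectories of all CYP presenting to the service".

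The operational sections are wider.

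- Section 3.4: for new cases, baseline is "defined as just before the first appointment, on the day of the first appointment, or within five months of the first appointment".
- Section 3.4 also lets those who decline or defer join later. They "may join PATHWAYS HORIZON at a later date, which will include baseline characterisation". No window is attached to that.
- Section 3.3, step 6: "There is no upper time limit for CYP and their parents/carers/legal guardians to consider participation".
- Section 3.3, step 1: the invitation to be contacted "will be sent separately for those who have already attended a first appointment".
- Section 3.1: CYP who attended and were "discharged prior to the study onset will also be contacted to provide them with the opportunity to participate". Section 3.3, step 4, describes this group as small.

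Table 1 has a single Baseline column. The fixed effects named in section 8.4.1 are timepoint, gender incongruence, age, site and neurodevelopmental conditions. Section 8.11 plans no sensitivity analyses. The one mentioned in section 8.8 concerns data missing not at random, which is a different question.

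**The concern.** Section 1.2 describes care as a sequence: assessment, formulation, a plan agreed with the family, then intervention. A questionnaire completed weeks or months after the first appointment may come after the plan was agreed or care had started. One completed after discharge certainly comes after that episode of care. If all such forms are tabulated as presenting status, the description is of a mixture and not of CYP as they arrive.

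Timing is also unlikely to be random. Section 3.3 lets families wait until after the first appointment to decide. It has staff follow up non-responders at that appointment. Where a parent does not consent, it considers a young person's capacity only once they have been assessed. Late forms will therefore come disproportionately from particular families, and a timing effect could be mistaken for a difference between types of family, or the reverse.

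The exposed measures are those that come only from questionnaires and can change over months: KIDSCREEN-10 (the primary outcome), RCADS, UGDS-GS and BIS-GS.

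**Working it through.** The protocol has no figure of its own to reproduce here. The check is a comparison of the timing rules, some window arithmetic, and an illustration on assumed inputs.

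**1. When the baseline questionnaire can fall, relative to the first appointment**

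| Route into the study | Earliest | Latest | Source |
|---|---|---|---|
| New case | just before | +5 months | section 3.4 |
| Declined or deferred, then joined | not stated | no limit stated | sections 3.3 and 3.4 |
| Discharged before study onset | after discharge | no limit stated | sections 3.1 and 3.3 |

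Only forms completed on or before the first appointment clearly match the descriptions in sections 1.2, 2 and 3.1.

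**2. Whether the timepoint label separates them**

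Section 3.4.1 anchors annual visits on the first assessment, with a window from 6 weeks before to 5 months after the annual date.

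- 6 weeks = 42 / 30.44 = 1.38 months.
- The month-12 window therefore runs from 12 - 1.38 = 10.6 months to 12 + 5 = 17.0 months after the first assessment.
- Taking the first appointment as that assessment, a new case with baseline at +5 months could give month-12 data 10.6 - 5 = 5.6 months later. One with baseline on the day could give it 17.0 months later.
- A deferred joiner, with no limit, could give baseline data when others are giving month-12 data.

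A categorical timepoint gives all these first questionnaires the same value. None of the other named fixed effects measures time since the first appointment or care status.

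**3. Illustrative size**

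Assumptions, neither given in the protocol:

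- p, the share of first questionnaires completed late enough for scores to have moved: 10% to 40%.
- d, the average movement by then: 0.1 to 0.3 SD.

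Error in the mean described as presenting = p x d.

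| | d = 0.1 SD | d = 0.3 SD |
|---|---|---|
| p = 10% | 0.01 SD | 0.03 SD |
| p = 40% | 0.04 SD | 0.12 SD |

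If all 3600 participants in section 8.3 gave data, the standard error of a mean would be 1/sqrt(3600) = 0.0167 SD. The error is then 0.01/0.0167 = 0.6 to 0.12/0.0167 = 7.2 standard errors. The low end would be lost in sampling noise and the high end would not. The protocol does not say where in this range the study would lie, or in which direction scores would move.

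**The case against.** Several points on the other side stand.

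- **Invitations are early by default.** Section 3.3 says the approach ordinarily goes out with the first-appointment information, so many baselines may be early. Section 2 openly says families may join later.
- **Five months is not shown to be after care.** The protocol does not say when intervention starts. Only the discharged group is certainly late, and it is small.
- **The medical history is safe.** Section 4.4.1.1 has clinicians record ten structured domains at the initial assessment. SNAP-IV and SCQ, as neurodevelopmental screens, should also be less sensitive to delay.
- **The SAP may handle this.** Section 8 never uses the word baseline. Section 4.3.2 captures the first-appointment date, so the SAP could classify timing.

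These points limit the concern but do not remove it. The mismatch between sections 1.2, 2 and 3.1 on one side and section 3.4 on the other lies in the protocol itself. So do the named model terms and the statement that no sensitivity analyses are planned.

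A reader might go further and infer that late baselines reverse cause and effect in a planned analysis of how presenting scores relate to later therapy, and so weaken that association. The protocol does not support this. Section 1.2 says only that characteristics may influence choices. Section 8.4 plans tests of outcomes against demographics, and therapy referral and uptake are binary outcomes with the primary model's covariates. No stated analysis compares baseline scores by later therapy, so no attenuation can be claimed. Nor does primary objective 1, which concerns care needs and developmental journeys, by its wording require values from before care. The statement of purpose in section 3.1 is what makes presenting status matter.

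**Conclusion.** The point holds in limited form. The protocol describes measurement at presentation but defines a baseline that can come well after it, and the named model terms do not tell the cases apart. Questionnaire values offered as presenting status may therefore be a mixture. This does not extend to the clinician-recorded history.

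The size is unknown. The range of 0.01 to 0.12 SD in the mean rests wholly on the assumed share and movement, and its top end needs both to be at their maximum. That most late forms follow the start of care is also not established. The change is still worth making, because it is cheap and is best fixed before data are seen: deciding afterwards which baselines count as presenting would be a post hoc choice.

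**What to change.** 1. Reconcile sections 1.2, 2 and 3.1 with section 3.4, so that the protocol says plainly what baseline represents for new, deferred and discharged participants.
2. Record the date each questionnaire was completed. Section 5.1.3 allows paper forms to be transcribed later, so the system's entry time is not always the completion date.
3. Classify each first questionnaire as (a) on or before the first appointment, (b) after it while in the service, with the lag in days, or (c) after discharge.
4. Report tables of presenting characteristics overall and by class, and do not describe class (c) as presenting status.
5. Add the timing class, or time since first appointment, to the section 8.4.1 model.
6. Repeat the presenting-characteristics analysis on class (a), or on (a) plus a stated short lag, as a sensitivity analysis, and amend section 8.11 to match. It should not be the only analysis: families who defer as section 3.3 allows would drop out, which works against describing everyone who presents.

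The cost is one completion-date field where it is not already held, and some extra analysis. The first-appointment date is already on the eligibility form. The restricted set will be smaller and selected, and should be reported as such.
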